When the subject has been fully examined and receives the final tumor diagnosis from the histopathology/PAD results (melanoma/non melanoma), the degree of agreement between the PAD and the outcome of the AI SW decision support is calculated with the Kappa-analysis and the diagnostic accuracy to be able to distinguish melanoma from non-melanoma in the form of sensitivity and specificity as well the positive and predictive value. The corresponding comparison is performed from the examining investigators' estimated clinical degree of suspicion, as well as the diagnostic accuracy when both the PAD and the AI decision support are weighted together (i.e. in cases where the investigator and the decision support are in agreement in their assessment). The clinical investigation will collect information from the users, how participating users (investigators at the site) experience the usability of the AI SW decision support and attaching applications, from short surveys including the validated System Usability Scale.

Use the same overall description given in Section 9.1.

Duration of exposure to the Investigational Medical Device

The subjects will not be in any direct contact with IMD Dermalyzer.

Duration of subjects' involvement in the investigation

The subjects will only perform 1 visit at a primary care centre to assess the cutaneous lesion(s).

Clinical performance assessments

The subject will be examined according to clinical routine. The cutaneous lesions where MM cannot be ruled out (study lesions) will be photographed with a digital dermatoscope. The digital image will then be able to be instantly uploaded to the study's AI enhanced web application (Dermalyzer), where the AI algorithm performs the image analysis within a few seconds.

Template Doc. id. Version

02

CIP Template QMS 12-01-

Document	Doc. id.	Version	Page
Clinical investigation Plan / Investigation code- AI-DSMM/	GR 21- 023	01	12 (52)

Clinical safety assessments

All considered reportable events in accordance with MDR, will be captured. The subject included in the investigation will follow the standard of care. The use of the AI will not influence the subject or the medical care of the subject.

Statistical methods

The sample size of at least eligible 239 lesions is calculated by an expected true proportion of 95% with 80% power. The estimated frequency of actual found malignant melanoma is 4.65% (or 12 MM out of 239 lesions).

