9.3.2 Number of subjects

To reach the target of 239 eligible lesions with a PAD approximately 500 lesions will need to be included, that is up to 500 subjects. The CI needs to be able to analyse 239 PAD verified lesions where at least 12 lesions need to be PAD positive responses (confirmed MM). In case, after 500 subjects/lesions have been evaluated and the 12 positive PAD have not been obtained, further subject enrolment will continue until 12 positive PAD have been reached.

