9.7.3 Analysis of clinical performance

9.7.3.1 Primary Objective and Endpoint

The primary objective of the investigation is to determine the diagnostic precision of the device; to answer at which level the AI tool Dermalyzer can identify malignant melanomas among cutaneous lesions that are assessed in clinical use due to any degree of malignancy suspicion.

The primary endpoint will be measured as the true proportion; by testing if the device based on artificial intelligence (AI) gives correct results as compared with the result of the lesion analysis (the final classification by PAD) in at least a certain proportion (π) of the analyses.

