9.7.6 Determination of sample size

The general practitioner (GP) will only include subjects in the investigation with lesions where melanoma cannot be ruled out. All lesions where melanoma cannot be ruled out will be sent for an analysis (final classification) to confirm – or not confirm – if the suspected melanoma is a melanoma or not. Each lesion where melanoma cannot be ruled out will be analysed by the IMD and the IMD will classify each lesion where melanoma cannot be ruled out as "Low Risk of being a melanoma" (Low) or "High risk of being a melanoma" (High).

In Table 1 the possible outcomes are described and (A+D)/(A+B+C+D) is the proportion of correct classifications by the IMD.

Template Doc. id. Version

CIP Template QMS 12-01- 02
01

Document Doc. id. Version Page

Clinical investigation Plan / Investigation code- AI-DSMM/ GR 21- 023 01 40 (52)

Table 1 Outcome (m = number of patients) for a binary variable where two groups of observations are linked together.					
			The Al device		
		High	Low	Total	
Final classification	Melanoma	А	В	A+B	
	Not melanoma	С	D	C+D	
	Total	A+C	B+D	A+B+C+D	

The expected value of (A+D)/(A+B+C+D) is denoted π and then the hypotheses of interest are

 H_0 : $\pi \leq \pi_0$

 H_1 : $\pi > \pi_0$

The null-hypothesis (H₀) will be rejected if the one-sided p-value is less than a. If $\pi = \pi_1$ the power to reject H₀ should be β .

Typically, a = 2.5 % and β = 80 % or 90 %. The p-value will be calculated using the exact Binomial test.

In a successful investigation H_0 is rejected and then H_1 is accepted.

Document Doc. id. Version Page

Clinical investigation Plan / Investigation code- AI-DSMM/ GR 21- 023 01 41 (52)

In Table 2 the needed number of lesions is presented based on the formula above and for statistical power 90%.

Table 2	Number of lesions where melanoma cannot be ruled out needed to achieve 80% power to reject (i.e. get a one-sided p-value less than 2.5%) the null-hypothesis by proportions to be rejected (i.e., π_0) and by assumed true proportions (i.e. π_1). Calculated by Sample Size a single proportion V01.xls.					
True Proportion (π ₁)		Р	roportion to b	oe rejected (π	:0)	
(71)	50%	60%	70%	80%	90%	95%
55%	783					
60%	194					
65%	85	742				·
70%	47	182				
75%	29	78	638			
80%	20	43	153			·
85%	14	26	64	471		·
90%	10	17	34	108		
95%	7	11	19	42	239	

Document			Doc. id.	Version	Page	
Clinical investigation Plan / Investigation code- AI-DSMM/		GR 21- 023	3 01	42 (52)		
100%	4	6	9	16	35	73

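### Section 9.7.6 introduces Table 2 as 90% power, but 239 lesions is the 80% figure (78% for the planned exact test); the synopsis equates 4.65% with 12 of 239, which is 5.0%

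*Combined protocol and SAP*

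**What the plan says.** Section 9.7.6 tests whether the proportion of lesions correctly classified by the device, π, exceeds a reference value π0. It gives the power for the sample size table in two ways:

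- The sentence before Table 2: "In Table 2 the needed number of lesions is presented based on the formula above and for statistical power 90" percent.
- The caption of Table 2: "needed to achieve 80% power to reject (i.e. get a one-sided p-value less than 2.5" percent.

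The synopsis (Statistical methods) agrees with the caption: "The sample size of at least eligible 239 lesions is calculated by an expected true proportion of 95% with 80% power". An earlier line in 9.7.6 names 80% and 90% as typical choices and selects neither. On the test itself, 9.7.6 states: "The p-value will be calculated using the exact Binomial test".

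The value of π0 behind 239 is not given in any sentence. Section 9.7.3.1 says only that the device should be correct "in at least a certain proportion" of the analyses. The number 239 appears in one cell of Table 2, in the row for a true proportion of 95% and the column for a rejected proportion of 90%.

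On melanoma yield, the synopsis says: "The estimated frequency of actual found malignant melanoma is 4.65% (or 12 MM out of 239 lesions". Section 9.3.2 makes 12 confirmed melanomas a requirement. If they have not been found after 500 subjects or lesions, "further subject enrolment will continue until 12 positive PAD have been reached". Section 11.2 repeats the 12.

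**The concern.** The lead-in sentence and the caption cannot both describe the same table. A reader who relies on the prose of 9.7.6 would take the risk of missing a true 95% accuracy to be 10%, when the design carries about 20%. The protocol calls the investigation confirmatory and pivotal, so its stated power should be the power it has, and the proportion to be rejected should be written down.

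The melanoma figures raise a smaller point of the same kind. The count of 12 is an enrolment requirement, and the synopsis presents it as equivalent to a frequency that does not yield it.

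**Working it through.** **Inputs.** One-sided α = 2.5% (Table 2 caption); π1 = 95% (synopsis and the 239 cell); π0 = 90% (inferred from the column of the 239 cell); power 80% (caption, synopsis) or 90% (lead-in sentence); melanoma frequency 4.65% and count 12 of 239 (synopsis); 239 verified lesions out of about 500 included (9.3.2).

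**1. Reproducing 239.** One-sample normal approximation, with the null variance under α and the alternative variance under power, rounded up:

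n = [z(1−α)·√(π0(1−π0)) + z(power)·√(π1(1−π1))]² / (π1−π0)²

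- 80% power: [1.960·√0.09 + 0.8416·√0.0475]² / 0.05² = [0.5880 + 0.1834]² / 0.0025 = 238.03, so **239**.
- 90% power: [0.5880 + 1.2816·√0.0475]² / 0.0025 = [0.5880 + 0.2793]² / 0.0025 = 300.88, so **301**, which is 62 more.

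**2. The rest of Table 2.** The same formula for all 31 filled cells:

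| Power | Cells with π1 < 100% (25) | Cells with π1 = 100% (6) |
|---|---|---|
| 80% | 25 match | 6 match |
| 90% | 0 match | 6 match |

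In the π1 = 100% row the alternative variance is zero, so power has no effect and those cells cannot tell the two readings apart.

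One coincidence needs ruling out. One-sided 5% with 90% power also gives 239 in this cell (238.87). The caption states 2.5%, however, and the alternative fails elsewhere. For 55% against 50% it gives [1.645·0.5 + 1.2816·√0.2475]² / 0.0025 = 852.6, so 853, where the table has 783.

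**3. Power of the planned exact test at n = 239.** With π0 = 0.90, 225 or more correct has probability 0.0162 under the null; 224 or more has 0.0293, which exceeds 0.025. The rule is therefore to reject at 225 or more, with attained size 1.6%. Under π1 = 0.95, P(X ≥ 225) = 0.781. The normal approximation gives 0.802.

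Exact power moves in a saw-tooth with n: 81.6% at 231, 78.1% at 239, 76.7% at 242, 83.9% at 243. It stays at or above 80% from n = 255 and at or above 90% from n = 316.

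**4. Melanoma frequency and count.**

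- 239 × 0.0465 = 11.11.
- 12 / 239 = 5.02%.
- 12 / 0.0465 = 258.

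With 239 verified lesions at 4.65%, the binomial probability of 12 or more melanomas is 0.435, and of fewer than 12 is 0.565. The probability of 12 or more reaches 80% at 316 verified lesions and 90% at 355. The plan expects a result for 239/500 = 47.8% of included lesions.

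**The case against.** The strongest reply is that little depends on this. The wrong 90% is one phrase. The caption below it, the synopsis and every informative cell say 80%, and the correction changes neither the sample size nor a rule. That is fair on consequence, but the phrase still misstates the power of a pivotal study in the section where a reader looks for it.

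A second reply is that 78% is one point on a saw-tooth, and that the number analysed is unlikely to be exactly 239, because the synopsis says at least 239 and about 500 lesions are to be included. Exact power is 88% at 300 and 97% at 400. This stands as a reason not to treat 239 as a wrong size. It does not remove the case for saying that Table 2 holds approximate values when the planned test is exact. The lead-in refers to a formula above the table that does not appear in the text available for this review. If the original shows it, the method may already be visible there.

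Third, the 57% chance of fewer than 12 melanomas depends on two assumptions: that only 239 of 500 lesions are verified, and that 4.65% applies to verified lesions. Section 9.7.6 also says all such lesions will be sent for final classification. With 500 verified lesions at 4.65%, the chance of fewer than 12 is 0.3%. The range is therefore about 0.3% to 57%. The upper end follows the plan's own figures, since the synopsis attaches 4.65% to the 239 lesions and 9.3.2 expects 239 verified out of about 500. In either case the continuation rule in 9.3.2 already covers a shortfall.

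Finally, 12 may be 11.1 rounded up, or may come from a base of 258 lesions (12/258 = 4.65%). The documents do not say, which is why the pair needs reconciling.

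**Conclusion.** The point holds. The 90% in the lead-in to Table 2 is wrong as written: 239 is the 80% figure, and 90% power would need 301 by the same formula. For the planned exact test, power at exactly 239 lesions is 78.1%. The shortfall of about 2 points comes from normal-approximation sizing and binomial discreteness, and is no reason to change the target. These figures rest on π0 = 90%, which is inferred from the table cell because no sentence states it.

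The synopsis frequency and count also disagree: 11.1 expected melanomas against 12, or 5.02% against 4.65%. On the plan's figures, the continuation rule is more likely than not to be needed (57%) if 239 of 500 lesions are verified, and becomes less likely as more are. Both errors should be corrected; neither means that the design fails.

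**What to change.** - **Section 9.7.6, sentence before Table 2:** state the power as 80% by normal approximation, and 78% for the exact binomial test at n = 239.
- **Table 2:** label the entries as normal-approximation values.
- **Section 9.7.6, text:** state the π0 used for 239. This is 90% if the table cell is what the sponsor intended; the sponsor should confirm.
- **Synopsis:** make the frequency and the count agree, either as 4.65% with about 11 melanomas expected among 239 lesions, or as 5.0% (12 of 239). The first leaves the estimated frequency untouched. The second changes an input, so it needs a source.

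Leave the target of 239, the Table 2 values, the minimum of 12 and the enrolment rules in 9.3.2 and 11.2 unchanged. The cost is a few lines of wording and a slightly less favourable stated power. No patients are added.

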8.1.1 Primary endpoint

The primary endpoint will be measured as the true proportion; by testing if the device based on artificial intelligence (AI) gives correct results as compared with the result of the lesion analysis (the final classification by PAD) in at least a certain proportion (π) of the analyses.

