The set expectation of 95% true proportion is based on in-silico experiments on a proprietary dataset of images which found a sensitivity of 95.1 \pm 0.6%.

The accuracy of AI decision support will be measured against gold standard (PAD) as well as against experienced dermatologists and general practitioners (average) and verified at: sensitivity> 95%, specificity> 75%, numbers needed to excise (NNE) <7, positive predictive value (PPV))> 15% and negative predictive value (NPV)> 99.5%. The average sensitivity for general practitioners in previous meta-analyzes is estimated at about 81%.

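### The 95% accuracy behind the 239 lesions rests on a sensitivity; 80% power in fact needs a specificity of about 95%, for which the CIP gives no estimate

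*Combined protocol and SAP*

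**What the plan says.** - **Endpoint.** Section 8.1.1 asks whether the device agrees with histopathology (PAD) "in at least a certain proportion (π) of the analyses". Section 9.7.6 makes this precise: ("A+D)/(A+B+C+D) is the proportion of correct classifications by the IMD"). This is overall accuracy, π, tested as H0: π ≤ π0 with a one-sided exact binomial test.
- **Planning value.** The synopsis states: "The sample size of at least eligible 239 lesions is calculated by an expected true proportion of 95% with 80% power". Section 9.7.6 gives the source: "The set expectation of 95% true proportion is based on in-silico experiments on a proprietary dataset of images which found a sensitivity of" 95.1 ± 0.6%.
- **Prevalence.** From the synopsis: "The estimated frequency of actual found malignant melanoma is 4.65% (or 12 MM out of 239 lesions").
- **Specificity.** The only figure is in a list of performance levels in section 9.7.6, "verified at: sensitivity> 95%, specificity> 75%, numbers needed to excise (NNE) <7", followed by PPV above 15% and NPV above 99.5%.
- **Null value.** π0 is not given in words. The number 239 appears once in Table 2, in the row for 95% and the column for 90%.
- **Power.** Section 9.7.6 says "Typically, a = 2.5 % and β = 80 % or 90" per cent, and then "In Table 2 the needed number of lesions is presented based on the formula above and for statistical power 90" per cent. The title of Table 2 and the synopsis both say 80%.

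**The concern.** Sensitivity is A/(A+B) in the notation of Table 1; the tested quantity is (A+D)/(A+B+C+D). A sensitivity of 95% tells us almost nothing about accuracy when about 19 of every 20 lesions are not melanoma. The 80% power then depends on a specificity that the CIP neither states nor sources.

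Two different failures are possible. With specificity between about 90% and 95%, the device beats the null but the study is underpowered at 239, and more evaluable lesions would help. With specificity below about 89.8%, the null is true and no sample size helps. The second case includes devices that satisfy all the listed performance targets, and the CIP does not say how those targets relate to its definition of a successful investigation, which is rejection of H0.

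**Working it through.** **Inputs.** π1 = 95% and 80% power (synopsis); π0 = 90% (inferred from Table 2); one-sided α = 2.5% and exact binomial test (9.7.6); sensitivity 95.1% (9.7.6); prevalence 4.65% (synopsis). The synopsis's alternative, 12/239 = 5.02%, leaves every power below unchanged to the whole percent.

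**1. The plan's own figure.** By the normal approximation,

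n = [(1.96·√(0.90·0.10) + 0.8416·√(0.95·0.05)) / 0.05]² = 238.03, rounded up to **239**.

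At 90% power the same formula gives 300.88, so 301. The 80% version reproduces every Table 2 cell for π1 from 55% to 95%. Table 2 is therefore an 80% table, and the sentence introducing it as 90% is wrong.

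**2. The planned test at n = 239.** The exact test rejects with at least 225 correct (at most 14 errors). Its size is 0.0162 and its power at π = 95% is 0.781.

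**3. Accuracy in terms of specificity.**

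π = 0.0465 × 0.951 + 0.9535 × specificity

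| Specificity | Accuracy | Exact power, n = 239 | Exact power, n = 500 |
|---|---|---|---|
| 90% | 90.24% | 2% | – |
| 91% | 91.19% | 6% | – |
| 92% | 92.14% | 15% | 33% |
| 93% | 93.10% | 32% | 65% |
| 94% | 94.05% | 55% | 90% |
| 95% | 95.00% | 78% | 99% |
| 96% | 95.96% | 94% | – |

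The n = 500 column (at least 464 correct) supposes that every enrolled lesion is evaluable. Exact power of 80% at n = 239 needs accuracy of 95.09%, which is a specificity of 95.1%. With perfect sensitivity the requirement falls only to 94.8%.

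**4. Where the null begins.** Accuracy equals 90% at specificity (0.90 − 0.0465 × 0.951)/0.9535 = 89.8%. For π0 = 80% the boundary would be 79.3%, and for π0 = 70% it would be 68.8%.

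**5. The listed targets.** At 80% specificity and 95.1% sensitivity:

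- PPV = 0.0442/(0.0442 + 0.9535 × 0.20) = 18.8%
- NNE = 1/0.188 = 5.3
- NPV = 0.7628/(0.7628 + 0.0465 × 0.049) = 99.7%
- Accuracy = 80.7%

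Every target is met and H0 is true. At 85% specificity the result is the same, with accuracy 85.5%.

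**6. Evaluable lesions for 80% power.**

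| Specificity | Plan's formula | Exact test, power stays at 80% or more from |
|---|---|---|
| 94% | 378 | 399 |
| 93% | 670 | 697 |
| 92% | 1443 | 1488 |

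**The case against.** Nothing is miscalculated: 239 follows from its inputs, and an unsourced planning value is not thereby a wrong one. Nothing in the text shows that specificity is below 95%; the 75% figure is a floor, not an expectation, so the low-power rows are scenarios and not forecasts. This stands, and it is why the point concerns an unsupported assumption and not a wrong sample size.

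A specificity might also be recorded elsewhere. Section 9.7.3.2 refers to a SAP for further analyses, and the in-silico work is reported in one sentence. The statement that no estimate is given applies to the text reviewed. Section 9.7.6 is nevertheless where the justification belongs, and what it offers there is a sensitivity.

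The 239 is a minimum, and about 500 lesions are to be enrolled. More evaluable lesions would help: at 94% specificity, 500 would give 90% power. But sections 9.3.2 and 11.2 plan for 239 evaluable from about 500, and extend enrolment only to reach 12 melanomas, so 239 is the fair planning case.

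Finally, the exact power of 78% partly reflects binomial discreteness: it is 80.4% at n = 234 and 83.9% at n = 243. That is correct. The 78% and the 225 threshold hold only at exactly 239 lesions, and the two-point shortfall is not itself the concern.

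**Conclusion.** The concern holds and should be fixed. The planning value for overall accuracy is justified by a sensitivity that bears on about 12 of 239 lesions. About 80% power requires a specificity of roughly 95% (94.8% to 95.1% as sensitivity goes from 100% to 95.1%). Each point lost from 95% down to 92% costs about 16 to 24 percentage points of power at 239 lesions.

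This rests on π0 = 90%, which is inferred, and on the plan's own prevalence and in-silico sensitivity. The 75% specificity target does not contradict the primary hypothesis, but the two standards are unreconciled. The 90% power sentence is a separate wording error with no effect on the design.

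**What to change.** In section 9.7.6 and the synopsis:

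1. State π0 explicitly; the position of 239 in Table 2 implies 90%.
2. Replace the sensitivity-based justification with π1 = prevalence × sensitivity + (1 − prevalence) × specificity, giving each assumed value and the source of the specificity.
3. Report exact power at n = 239 for specificity 90% to 96% (2, 6, 15, 32, 55, 78 and 94%), and state that specificity below about 89.8% lies within H0.
4. Add a sentence on how the 75% specificity target relates to primary success. If π0 = 90%, success means at least 225 of 239 correct, with the exact test applied to the number actually evaluable.
5. Change the power in the sentence before Table 2 to 80%, note that exact power at n = 239 is 78%, and replace the list of typical values with the α and power chosen.

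Items 1, 3, 4 and 5 are recalculation and wording. Item 2 needs a specificity figure, perhaps from the in-silico experiments if they recorded one. If it lies between about 90% and 95%, the sponsor must accept lower power or raise the target. At 94%, 378 evaluable lesions by the plan's formula means 378/(239/500) = 791 enrolled; the exact-test figure of 399 means about 835. If it lies below about 89.8%, π0 itself has to be reconsidered, which changes the hypothesis. The drawback is that the stated power becomes less favourable and openly conditional on specificity.

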11.2 Time table

The end of the clinical part of the investigation is defined as the enrolment of approximately 500 lesions where MM could not be ruled out, to reach the target of 239 evaluable (having PAD outcome result) lesions, with 12 positive PAD results. It is estimated that the PAD results will come from the laboratory within approximately 2 months time frame from each excision.

The enrolment period of the investigation is expected to start in Quarter 1, 2022 and to be completed by Quarter 3, 2022.

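### Sensitivity >95% and NPV >99.5% are to be verified with no stated rule; at 12 melanomas among 239 lesions, even perfect results have exact 95% lower limits of only 73.5% and 98.4%

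*Combined protocol and SAP*

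**What the plan says.** Section 9.7.6 ends by stating that accuracy, measured against histopathology (PAD) and against dermatologists and general practitioners, will be "verified at: sensitivity> 95%, specificity> 75%, numbers needed to excise (NNE) <7", then PPV above 15% "and negative predictive value (NPV)> 99.5"%. No hypothesis, confidence level, interval method or success rule accompanies any of the five.

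The same section specifies one test, on the overall proportion of correct classifications, (A+D)/(A+B+C+D). "The p-value will be calculated using the exact Binomial test", and the caption of Table 2 defines rejection ("i.e. get a one-sided p-value less than 2.5"%). The 239 lesions come from the Table 2 cell with 90% to be rejected and 95% assumed true.

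On numbers, section 9.3.2 calls for "239 PAD verified lesions where at least 12 lesions need to be PAD positive responses (confirmed MM"), and lets enrolment run past 500 only until the twelfth melanoma is reached. Section 11.2 repeats the aim: "to reach the target of 239 evaluable (having PAD outcome result) lesions, with 12 positive PAD results".

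Three other places bear on the point. Section 9.7.1 presents binary data as counts and percentages. The synopsis, under Methodology, has sensitivity, specificity and predictive values calculated against PAD. Section 9.7.3.2 refers further analyses to an SAP, whose text is not part of the material available here.

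**The concern.** To say that a target is verified claims more than to say that a measure is estimated. Sensitivity and NPV are the two measures that speak directly to missed melanomas, section 9.7.4.1 names false negatives among the main risks, and the synopsis calls the investigation confirmatory and pivotal. Yet neither measure enters the sample size calculation, and the guaranteed number of melanomas is small. Under the present wording, 12 detected out of 12 could be reported as sensitivity above 95% verified, although the data would be compatible with a far lower value.

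**Working it through.** **Inputs.** Targets: sensitivity >95%, NPV >99.5% (9.7.6). Guaranteed minimum: 239 lesions with PAD, of which 12 are melanomas (9.3.2, 11.2), so 239 − 12 = 227 non-melanomas. Primary test: exact binomial, one-sided 2.5% (9.7.6). Confidence level for the two targets: not stated. I assume an exact (Clopper-Pearson) two-sided 95% limit, because its lower tail of 2.5% matches the primary test, and show a one-sided 95% limit as the lenient alternative. Lesions are treated as independent.

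**1. The plan's own figure.** Normal approximation, π0 = 0.90, π1 = 0.95, one-sided 2.5%, 80% power:

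n = [1.960·√(0.90·0.10) + 0.842·√(0.95·0.05)]² / 0.05² = 238.03, rounded up to 239.

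This reproduces Table 2. (At 90% power the formula gives 301, so 239 is the 80% figure in the table's caption, not the 90% mentioned in the sentence above it.) The calculation concerns overall agreement only; the number of melanomas does not enter it.

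**2. Best-case lower limits.** When all n are correct, the exact lower limit is 0.025^(1/n) for two-sided 95% and 0.05^(1/n) for one-sided 95%.

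| Result | Setting | Two-sided 95% | One-sided 95% | Target |
|---|---|---|---|---|
| Sensitivity 12/12 | 12 melanomas | 73.5% | 77.9% | 95% |
| NPV 227/227 | 239 lesions, 12 melanomas | 98.4% | 98.7% | 99.5% |
| NPV 488/488 | 500 lesions with PAD, 12 melanomas | 99.2% | 99.4% | 99.5% |

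Wilson two-sided 95% limits lead to the same conclusion: 75.8% for 12/12 and 98.3% for 227/227.

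The NPV rows assume that every non-melanoma is rated Low. At the 75% specificity target, about 0.75 × 227 = 170 would be, and 170/170 has a two-sided lower limit of 97.9%.

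If instead all of about 500 lesions had PAD at the synopsis frequency of 4.65% (0.0465 × 500 = 23.25, so about 23 melanomas and 477 others), the best cases are 85.2% for 23/23 and 99.2% for 477/477.

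**3. What would clear the targets with no miss.**
- Sensitivity: ln(0.025)/ln(0.95) = 71.9, so 72 melanomas (59 with a one-sided 95% limit).
- NPV: ln(0.025)/ln(0.995) = 735.9, so 736 Low ratings (598 with a one-sided 95% limit).

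**4. The point-estimate reading.** At 12 melanomas, 11/12 = 91.7% fails, so 12/12 is the only passing sensitivity result. Its probability is 0.90^12 = 0.282 at a true sensitivity of 90%, which is below target, and 0.95^12 = 0.540 at 95%. For NPV with one missed melanoma, 227/228 = 99.56% passes but 170/171 = 99.4% does not, so the outcome then turns on how many non-melanomas are rated Low.

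**5. Synopsis figures (minor).** 0.0465 × 239 = 11.1; 12/239 = 5.02%; 12/258 = 4.65%.

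**The case against.** The best defence is that these targets carry no formal weight. They are not among the endpoints in sections 8.1.1 and 8.2.1, success is defined only by rejecting the primary null hypothesis, and the device result does not alter care. Section 9.7.1 and the synopsis describe counts, percentages and calculated accuracy measures, so the natural reading is estimation, and on point estimates the targets can be met. The 95% limit used here is not the plan's, and the SAP may already define a rule.

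Much of this stands. The criterion is an assumption, and it cannot be said that the full plan lacks a rule. But section 9.7.6 still says verified, the shortfall appears under every limit tried, and no SAP rule can add precision on sensitivity to 12 melanomas.

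Three stronger readings are tempting and not supported:

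- A reader might infer that 12 melanomas fix the NPV limit at 98.4%, or that no permitted result could clear 99.5%. The limit depends on the number of Low ratings. Section 9.3.2 sets no cap on enrolment beyond 500, so 736 Low ratings with no miss are possible in principle. With only 12 melanomas that would mean a frequency of about 12/748 = 1.6%, well below the 4.65% expected.
- A reader might set the 73.5% against the sentence "The average sensitivity for general practitioners in previous meta-analyzes is estimated at about 81"% and conclude that the device could not be shown to beat general practitioners. The documents give that figure as background and plan no test against it. Investigators record their own assessment of the same lesions before seeing the device result (9.4.10).
- A reader might want specificity, PPV and NNE called verified only when a confidence limit clears the target. Nothing in the documents asks for that. With 12 true positives and 227 non-melanomas, PPV would need at most 31 false positives (12/43, lower limit 15.3%), which has about a 32% chance at a true specificity of 85%.

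**Conclusion.** The concern holds as a fault in what section 9.7.6 promises. At the guaranteed minimum of 12 melanomas, no result gives an exact 95% lower limit for sensitivity above 73.5% (77.9% one-sided), against a target of 95%. At 239 lesions including 12 melanomas, none gives a limit for NPV above 98.4%, against 99.5%. Reading the targets as point estimates rescues the wording only in form, since sensitivity then rests on a single passing result that a device at 90% would produce 28% of the time.

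This depends on the assumed exact 95% limit and on independence between lesions. The NPV figure also depends on 227 non-melanomas all being rated Low. The absence of a rule is established for section 9.7.6 and the text available, not for the SAP.

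A reader might take the narrow scope as reassurance about the primary test. None is intended: rating every lesion Low at 12 melanomas in 239 gives 227 correct, against the 225 needed to reject 90%, with a sensitivity of zero. Overall agreement therefore cannot stand in for evidence on missed melanomas, which is why the sensitivity and NPV statements should be worded with care.

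**What to change.** In section 9.7.6, replace the verification wording for all five measures with text such as: *Sensitivity, specificity, NNE, PPV and NPV will be estimated, with exact 95% CIs, and compared descriptively with the targets. With the minimum of 12 melanomas, the best-case lower 95% limit for sensitivity is 73.5%; with 227 non-melanomas, the best-case lower limit for NPV is 98.4%.* If the SAP already gives intervals or a rule, refer to it there and make the two agree.

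This costs a few sentences and no extra enrolment. The downside is a less favourable statement of what the investigation can conclude.

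Minor: the sponsor should reconcile the 4.65% and the 12 of 239 in the synopsis. The 12 may be 11.1 rounded up, but the documents do not say so.
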